4. STUDY OBJECTIVES

4.1 Overall Objective

The overall objective of this study is to investigate if the modulation of the information when inserting a PIC in the ED has an impact on patients' pain and anxiety levels and if this effect is comparable, whether the message is delivered through a standardized audio recording or directly by caregivers. It also explores if there are differences in patients' and caregivers' assessments of pain and anxiety.

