4.3 Secondary Objectives

Secondarily, this study aims to explore the effect of the intervention on patients' anxiety.

Finally, it seeks to explore the differences that may exist between an assessment of pain and anxiety made by patients (feelings of pain and anxiety) and that made by caregivers (estimated pain and anxiety) as well as the possible determinants of these differences, if they exist (patients: sex, age, origin, level of education / caregivers: sex, age).

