9.2 Assessments of outcomes

9.2.1 Assessment of primary and secondary outcomes

The primary outcomes, the intensity and unpleasantness (emotional component) of pain experienced by patients during the PIC insertion, will be measured using a Visual Analog Scale (VAS) (Lang et al., 2014; Pagé et al., 2012). Patients' anxiety, as a secondary outcome, will also be measured by VAS. These three measurements will be performed by using three rulers after the PIC is inserted. These three rulers, with three different color codes to distinguish them, will be presented to the patients who will move the three sliders on a line going from one extreme to the other (No pain / Worst pain imaginable; Experience not at all unpleasant / Most unpleasant experience possible; Not at all anxious / Extremely anxious) and corresponding, on their other side, to a value between 0 and 100 mm on a 100 mm long line. This numerical value measured in millimetres will be reported in the CRF by the co-investigators. Patients will be asked to rate their overall feelings after the PIC insertion regarding these three aspects. The co-investigators will ensure that the caregivers do not become aware of the patients' responses.

As for caregivers' assessment of patients' pain intensity and unpleasantness and anxiety, these secondary outcomes will also be measured using the three VAS, this time in paper format and reported in the CRF after the PIC insertion. Caregivers will mark their estimation by tracing a line on each of the three VAS once they have completed their procedure, making sure that patients do not read their answers. The co-investigators will then measure the distance between the 0 extreme and the line traced by the caregivers in millimetres and report this numerical value in the CRF.

Before the PIC insertion, patients will assess the intensity and unpleasantness of any pre-existing pain and their basal anxiety level with these same three VAS. This will give a baseline value for these three measures. These values will be reported in the CRF before the PIC is inserted, along with the reason for consultation (internal medicine, traumatology or surgery) and any painkillers already given/ongoing in the ED.

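### Patients rate on slider rulers and caregivers on paper lines, so the mean patient-minus-caregiver difference mixes a rater effect with a format effect

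*Combined protocol and SAP*

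**What the plan says.** The instruments are described in section 9.2.1 and, more briefly, under outcomes in the synopsis.

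- **Patients.** "These three measurements will be performed by using three rulers after the PIC is inserted". On the response mode: "These three rulers, with three different color codes to distinguish them, will be presented to the patients who will move the three sliders on a" scale, which corresponds on the reverse side to "a value between 0 and 100 mm on a 100 mm long line". The co-investigator enters the number in the CRF.
- **Caregivers.** For their estimates of the same three quantities, "these secondary outcomes will also be measured using the three VAS, this time in paper format". On the response mode: "Caregivers will mark their estimation by tracing a line on each of the three VAS once they have completed their procedure". On the reading of the mark: "The co-investigators will then measure the distance between the 0 extreme and the line traced by the caregivers in millimetres".

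Neither place distinguishes arms or phases, and the study schedule describes the two phases as alike apart from how the message is delivered. Every patient score therefore comes from a ruler and every caregiver score from paper.

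The comparison of the two raters is a stated aim. Section 4.1 says: "It also explores if there are differences in patients' and caregivers' assessments of pain and anxiety". Section 4.3 lists it among the secondary objectives: "it seeks to explore the differences that may exist between an assessment of pain and anxiety made by patients", compared with the caregivers' assessment, together with possible determinants (patient sex, age, origin and education; caregiver sex and age).

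**The concern.** When two raters are compared on a continuous scale, the usual safeguard is that both use the same instrument. Here the rater and the instrument change together. Moving a slider and reading a printed value is a different task from drawing a mark that someone else measures, and the two could differ systematically, for example through the slider's starting position or through the hand measurement.

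Any such offset would pass one-for-one into the mean patient-minus-caregiver difference. A report that caregivers under-rate or over-rate their patients' pain or anxiety by some number of millimetres could then owe part or all of that number to the format. Because no patient and no caregiver uses both formats, the trial's own data could not show how much.

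**Working it through.** **1. What the mean difference estimates.** Let R and C be the true mean patient and caregiver ratings, f_ruler the average shift due to the ruler and f_paper the average shift due to paper. Then

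mean(patient − caregiver) = (R − C) + (f_ruler − f_paper).

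Only the sum can be estimated. A larger sample narrows the interval around the sum but does not separate its parts.

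**2. Search for a safeguard.** The Rating pilot (section 9.2.1) covers caregiver behaviour and the Algoplus scale only. The Messages pilot (sections 6.2.3 and 8.4) covers the recordings. Section 11.4.3 gives a t-test or rank sum test for the caregiver ratings. It does not mention format and describes no paired analysis of patient against caregiver. No calibration of one format against the other is described.

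**3. What a constant offset leaves alone.**
- Between arms, for either rater: both arms share one format, so the shift cancels, for example (intervention + f_ruler) − (control + f_ruler). This covers the primary outcome and the arm comparison of caregiver ratings.
- The patient-caregiver gap compared between arms or phases: the offset is the same on both sides and cancels.
- Patient-caregiver correlation: adding a constant does not change it.
- Association of the gap with the listed determinants: the offset goes into the intercept, unless the format effect itself varies with a determinant.

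**4. The plan's own figure.** Section 11.2 gives 55 per arm for a 13 mm difference, SD 24 mm, 80% power and alpha 5%. With a two-sided test, n = 2 × (1.960 + 0.842)² × 24² / 13² = 53.5, or 54 per arm. The t-based solution is 54.48, rounded up to 55. The figure reproduces and does not depend on this point. The plan gives no precision for the patient-caregiver comparison.

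**5. How precise the mean difference would be.** Inputs:
- Pairs per phase: 120 randomised (2 × 60, section 11.2) less 10% = 108.
- SD 24 mm for each rater. Section 11.2 gives it for patients' pain intensity. Its use for caregivers, unpleasantness and anxiety is an assumption.
- Correlation between the two ratings of 0.2 to 0.6: assumed.
- Pairs treated as independent.

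SD of difference = 24 × √(2(1 − ρ)); half-width = t(107) × SD of difference / √108, with t = 1.98 and √108 = 10.39.

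| ρ | SD of difference (mm) | 95% half-width (mm) |
|---|---|---|
| 0.6 | 21.5 | 1.98 × 21.5 / 10.39 = 4.1 |
| 0.2 | 30.4 | 1.98 × 30.4 / 10.39 = 5.8 |

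With no true rater difference, an offset equal to the half-width would give p < 0.05 in about half of trials instead of 5%. As a second illustration, with ρ = 0.5 and 110 pairs (normal approximation), an assumed offset of 3 mm gives rejection in 26% of trials and one of 5 mm in 59%. With 240 pairs these become 49% and 90%. With no offset the rate stays at 5%.

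**6. Clustering.** Section 9.2.1 recognises that patients are clustered by caregiver. Positive clustering widens the interval. With an assumed 5 patients per caregiver and intraclass correlation 0.1, the design effect is 1 + 4 × 0.1 = 1.4, and the half-widths become about 4.8 to 6.9 mm (multiplying by √1.4 = 1.18).

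**The case against.** The strongest reply is that no harm is shown. Both formats are visual analogue scales scored in millimetres, nothing in the documents indicates a non-zero offset, and the calculation shows only how large one would have to be to matter. An offset of 4 to 6 mm is also less than half of the 13 mm that section 11.2 treats as the smallest clinically significant decrease in pain. That benchmark was set for a change in pain, not for a gap between raters, but it is the only one the plan offers. All of this stands, and it is why the point is minor. It does not remove the mixture: the plan offers nothing to show that the offset is small, and the trial could not measure it.

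Paper also has a merit. The caregiver's mark is a listed source document (section 12.1.2), and the monitor checks the main VAS values (section 12.3). That is a real cost of changing, though the patients' own scores already go from the ruler to the CRF without a paper mark. Keeping the ratings private does not require paper: section 9.2.1 already has the co-investigators keep patients' ruler responses from the caregivers.

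A reader might infer three stronger things that the documents do not support:
- **That the pain results of the trial are compromised.** They are not. Each rater uses one format in both arms.
- **That the whole patient-caregiver objective becomes uninterpretable.** Only the mean difference is affected by a constant offset. The correlation and the determinant analyses are not.
- **That the paper line differs in length from the ruler.** The text does not give its length, but the caregivers' form is Appendix 9, which is listed and not reproduced in the material reviewed. No defect can be inferred from that.

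**Conclusion.** The point holds in a limited form. In the mean patient-minus-caregiver difference, for all three scales and in both phases, rater and format cannot be told apart, and the plan contains no check that would separate them. This concerns one estimate within an exploratory secondary objective.

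The size of the bias is unknown. On the assumptions stated in the working, an offset of about 4.1 to 5.8 mm could by itself yield a statistically significant difference. With clustering by caregiver the offset would have to be larger. Statistical significance at that size would not by itself make the difference clinically meaningful. The sample size is unaffected. The change is worth making because it is cheap beforehand and the bias cannot be repaired once the data are collected.

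**What to change.** Have caregivers rate on the same type of slider ruler as patients. The sliders are reset before use and kept out of the patient's sight, and the co-investigator reads the value and records it in the CRF as for patients. Amend section 9.2.1, the outcomes entry of the synopsis, section 12.1.2 (which lists the caregivers' paper form as a source document) and Appendix 9.

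**Cost.** A second set of three rulers and the wording changes. No extra staff are needed, and neither the sample size nor the patients' procedures change. The downside is that the caregiver's own paper mark is no longer kept as a source document.

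If paper is kept for that reason, state in the analysis plan that the mean patient-minus-caregiver difference is to be read as rater plus format, and report this as a limitation.

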9.2.2 Assessment of safety outcomes

9.2.2.1 Adverse events

Any adverse event resulting from the intervention (i.e. procedural information), and not those arising from the reason for consultation in the ED, the care provided for this reason or the insertion of the PIC

(e.g. bleeding, hematoma), will be reported in the CRF and, if additional medical care has been required, reported to the CEC.

9.2.2.2 Laboratory parameters

Non-applicable.

9.2.2.3 Vital signs

Non-applicable.

9.2.3 Assessments in participants who prematurely stop the study

Participants who have revoked their consent or who are excluded from the study will have their data collected as part of the study destroyed, except for data relating to their sex and age, which will be kept for statistical purposes in a separate document (Appendices 7 and 8). They will be given a copy of the complete information sheet so that they can contact the investigators if they wish to do so.

9.3 Procedures at each visit

Non-applicable. Patients' participation in the study is unique. They will not be included in the first or second phase of the study if they are seen again in the ED.

10. SAFETY

As this study is part of a medical management context in an ED, adverse events resulting from the reason for consultation, the care provided for this reason or the PIC insertion (e.g. bleeding, hematoma) will not be reported as such in the CRF because they are independent of the study. Only adverse events directly resulting from the intervention (i.e. procedural information) will be reported in the CRF by the co-investigators and reported to the principal investigator within 2 hours. The CEC will also be informed within 2 days if preventive or corrective medical measures are necessary to protect the health and safety of the participants.

However, the risk of a specific adverse event for this very brief intervention that modulates only procedural information is very low or non-existent. Should any adverse event occur, it will be spontaneously reported in the CRF by the co-investigators during the intervention. In addition, participants will be actively questioned about any potential inconvenience to their participation during the debriefing phase. Finally, in order to ensure that any adverse events can also be reported after the end of the study, the complete information sheet containing the investigators contacts will also be handed out to all participants.

An annual safety report will be submitted to the CEC once a year.

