2.3 Competent Ethics Committee (CEC)

Investigators ensure that approval by an appropriate CEC has been obtained for this study. They will report to the CEC any serious adverse event within 7 days. They will also inform the CEC within 15 days in case of early termination or discontinuation of the study. The planned completion of the study will be report to the CEC within 90 days. A final report will be submitted within one year of the completion of the data collection, in the form of a Master's degree work.

No substantial amendments to the protocol shall be made without the prior approval of the CEC, except in cases where such changes would be necessary to address an immediate and apparent risk to study participants.

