After consulting the patient's medical records in the ED and checking with the patient's caregivers that there are no exclusion criteria, the co-investigators will introduce themselves to the patients and invite them to participate in the study. The co-investigators will explain to the patients that, given the fact that their medical care involves the insertion of a PIC, they are eligible for this study aimed at improving the care of patients visiting the LUH ED during such an act. Should patients require additional information, the co-investigators will simply state that the study's primary objective is to assess the technical characteristics of the PIC insertion. At this stage, only a verbal agreement will be required. After verifying that all inclusion criteria have been met, that none of the exclusion criteria are applicable and obtaining a verbal consent, patients will be randomized in a 1:1 ratio between the two arms of the study, in a double-blind design (patient, caregiver, co-investigator) in the first phase and in a single-blind design (patient) in the second phase. The co-investigators will collect some additional data in a standardized manner by following the CRF and then report to the caregivers that they can prepare the patients for PIC insertion (installation of the tourniquet, vein tracking and site disinfection). In the first phase, a test audio clip and a recorded introductory audio clip will be played to the patients before the caregivers prepare them for the procedure. Once these preparations are completed, the co-investigators will play the recorded audio intervention or control message to the patients in the first phase or the caregivers will deliver one of the two alternative messages directly before puncturing the patients' vein in the second phase. In both cases, the co-investigators will complete the collection of data according to the CRF, first from patients and then from caregivers. Once all the data has been collected, a complete information sheet and consent form will be provided to the patients, along with additional explanations when requested. Patients will have a minimum of 15 minutes to sign the consent form. Excluding this 15 minutes reflection period, participation in the study should not exceed 20 minutes and will be unique.

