6.2.2 Blinding procedures

During the first phase, the allocation of the arm « control message » or of the arm « intervention message » will be determined by a code written on a card inside a sealed and opaque envelope, prepared by the principal investigator. This code will indicate the number, between 1 and 130, of the audio track to be played to the patient and will be recorded in the CRF. In the second phase, the note « control message » or « intervention message » written on the card will indicate to the caregivers the message to be delivered and will be reported in the CRF. Envelopes will be numbered consecutively, and the co-investigators will open them consecutively, noting each time the opening date. The principal investigator will regularly verify that the order of opening is respected by checking the number of envelopes opened and the opening dates against the number of patients included in the study.

The first phase of the study will be carried out in double blind (patient, caregiver, co-investigator) thanks to the coding of audio recordings. In the second phase, only patients will be blinded to the tested component.

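### Sections 9.2.2.1 and 10 label an event as adverse, and send it to the ethics committee, only after attribution to the message, which contradicts the promise in section 2.3 to report any serious adverse event

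*Combined protocol and SAP*

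**What the plan says.** Four places in the combined protocol and SAP deal with reporting adverse events.

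- Section 2.3 makes an unconditional commitment: "They will report to the CEC any serious adverse event within 7 days".
- Section 3.7 says that events caused by the intervention are entered in the CRF and passed to the ethics committee where necessary. It gives no time.
- Section 9.2.2.1 limits recording to "Any adverse event resulting from the intervention (i.e. procedural information), and not those arising from the reason for consultation in the ED", and goes on to exclude events from the care given or from the insertion. Such an event is, "if additional medical care has been required, reported to the CEC". It gives no time.
- Section 10 repeats the limit: "Only adverse events directly resulting from the intervention (i.e. procedural information) will be reported in the CRF by the co-investigators". Events from the illness, its care or the insertion "will not be reported as such in the CRF because they are independent of the study". Recorded events go to the principal investigator within 2 hours, and the ethics committee is "informed within 2 days if preventive or corrective medical measures are necessary". The next paragraph of section 10 says, without qualification, that any adverse event that occurs will be recorded, and that participants will be asked at debriefing about inconveniences.

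On blinding, section 6.2.2 says of phase 2: "In the second phase, only patients will be blinded to the tested component". Safety objectives (4.4), safety outcomes (5.3) and the safety analysis (11.4.5) are all marked as not applicable.

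**The concern.** Two things are at stake.

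The first is a reporting duty that the plan cannot discharge as written. Section 2.3 promises the ethics committee every serious adverse event, while the operating instructions in 9.2.2.1 and 10 handle only those blamed on the message. A co-investigator who follows section 10 faithfully could leave a section 2.3 obligation unmet.

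The second is the order of steps: cause is judged first and the adverse-event label follows. Section 10 justifies this by treating insertion events as unconnected with the study. Yet section 11.1 hypothesises that the message changes the pain caused by the insertion, and section 3.1 argues that a warning can make pain and anxiety worse. If a patient faints or panics at the puncture, nobody at the bedside can reliably say whether the needle or the words were responsible. In phase 2 the person who has to say so also knows which words were used.

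**Working it through.** The plan states no figure on this point, so the check is mainly a comparison of text.

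**Step 1. The reporting rules side by side.**

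| Section | Trigger for the ethics committee | Must the message be the cause? | Time |
|---|---|---|---|
| 2.3 | Event is serious | No condition stated | 7 days |
| 3.7 | Forwarding is necessary | Yes | None given |
| 9.2.2.1 | Extra medical care was needed | Yes | None given |
| 10 | Protective or remedial medical action is needed | Yes, by context | 2 days |

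The 7-day and 2-day times have different triggers and can stand together. The row that cannot be squared with the others is 2.3, because of its scope.

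**Step 2. A test case.** Take a serious event after the puncture that the co-investigator puts down to the catheter.

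- Under 2.3 it goes to the ethics committee within 7 days.
- Under 9.2.2.1 and 10 it is not an adverse event for the CRF, so the 2-hour notice to the principal investigator and the step to the committee are not triggered.
- Under 5.2, 6.1 and 9.2.1 it can be written in the complications field among the procedure characteristics. No seriousness assessment and no onward reporting is attached to that field.

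The duty exists, but no route is stated.

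**Step 3. Section 10 against itself.** One sentence confines the CRF to events caused by the message, and a later one says any adverse event is recorded. The later one follows a remark about the low risk of an event specific to the intervention, and 3.7 has a near-identical sentence that does carry the causal condition. A narrow meaning may therefore have been intended, but the words of section 10 do not say so.

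**Step 4. Who decides, and what they know.** The plan names no separate assessor, so the decision falls to the co-investigator who makes the entry. In phase 1 coded audio tracks keep that person blind. In phase 2 the co-investigator opens an envelope whose card names the message (6.2.2) and ticks off its content as it is spoken (8.1.1). Phase 2 has two arms of 60: 2 × 60 = 120 of 240 patients.

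**Step 5. How far a phase 2 table could be distorted.** The documents give no event rate, so these are assumptions for illustration. Let the true rate *p* be the same in both arms, and let the recorder attribute a fraction *a* of control-arm events and *b* of intervention-arm events to the message. The expected recorded counts are 60·*p*·*a* and 60·*p*·*b*, with ratio *a*/*b*.

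| *p* | True events per arm | *a* = *b* = 50% | *a* = 60%, *b* = 40% | *a* = 80%, *b* = 20% |
|---|---|---|---|---|
| 2% | 1.2 | 0.6 v 0.6 | 0.72 v 0.48 | 0.96 v 0.24 |
| 5% | 3.0 | 1.5 v 1.5 | 1.8 v 1.2 | 2.4 v 0.6 |
| 10% | 6.0 | 3.0 v 3.0 | 3.6 v 2.4 | 4.8 v 1.2 |
| Ratio | 1 | 1 | 1.5 | 4 |

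With even-handed attribution there is no distortion. With uneven attribution a ratio of 1.5 to 4 can appear where none exists, but on very small counts.

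**The case against.** The best defence is that little information is lost and no result depends on it. Most of that stands.

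- A reader might infer that events blamed on the puncture vanish from the record. They do not. Section 10 keeps them from being labelled as adverse events, but complications are recorded for every patient (5.2, 6.1), inconveniences are a CRF item (6.1), and distress is captured by the unpleasantness and anxiety VAS and by Algoplus (9.2.1). None of these needs prior attribution.
- A reader might infer that a planned comparison is biased. None is: 4.4, 5.3 and 11.4.5 plan no safety comparison, and in phase 1 the recorder is blind.
- A reader might infer that the different reporting times contradict each other. They answer to different triggers.
- A reader might infer that patients cannot help to identify a message-related event, because full disclosure comes late: "Once all the data has been collected, a complete information sheet and consent form will be provided to the patients". But the study schedule marks adverse events in the debriefing column, alongside complete information, and section 10 gives every participant the information sheet with contact details for later reports.
- The intervention is a message of at most one minute in a risk category A study, so serious events should be rare.

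These points limit the consequences but leave the conflict in place. The complications field leads nowhere beyond the CRF, low expected risk does not say which of two rules to follow, and the adverse-event label still matters: the monitor checks adverse reactions (12.3) and annual safety reports are promised (2.5, 10).

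**Conclusion.** The reporting rules are wrong as written. Section 2.3 covers serious events whatever their cause. Sections 9.2.2.1 and 10 cover only events attributed to the message, and section 10 is inconsistent within itself. For a serious event put down to the illness, its care or the puncture, the plan states a duty but no route to the ethics committee. This applies in both phases.

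The statistical consequence is limited. No planned analysis is affected and the pain and anxiety outcomes are untouched. Any table of adverse events by arm in phase 2 (120 patients) could be biased, because a recorder who knows the arm controls the label. How much cannot be derived from the documents. The ratios of 1.5 to 4 above rest entirely on assumed event rates and attribution fractions, and do not show that such bias will occur.

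The conclusion assumes that the section 10 sentence on the ethics committee continues the restriction in the sentence before it, and that the co-investigator who makes the entry also makes the attribution. Both are the natural reading, but neither is spelled out.

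**What to change.** 1. In 9.2.2.1 and 10, record every untoward event from the start of the message until the consent form is signed, whatever its presumed cause, with a short description. Bring the matching sentence in 3.7 into line.
2. Make relatedness to the message a separate field, completed afterwards, and no longer a condition for recording. In phase 2 that judgement may still be made with the arm known, but it would no longer decide what is counted.
3. Replace the statements in 2.3, 9.2.2.1 and 10 with one consistent rule on which events go to the ethics committee, who sends them and by when. Which scope and times apply is for the sponsor and the committee to settle. The sections only have to agree.
4. In the same rule, say how it fits with 7.4. A patient who becomes unstable before signing is excluded and all data except sex and age are destroyed, which could remove the record of a reportable event.

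The cost is one CRF line and a short amendment. The recording window is brief: participation is capped at 20 minutes, plus a reflection period of at least 15 minutes. The downside is a few more minor puncture events to write down.
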